3 STUDY PROCEDURES

3.1 Study Participant Information and Informed Consent

The investigator or his/her representative will explain the nature of the study to the participant, the benefits and risks anticipated from participation in the study and answer all questions regarding this study. Prior to any study-related screening procedures being performed on the participant or any medications being discontinued by the participant in order to participate in this study, the informed consent statement will be reviewed, signed, and dated by the participant or their legally authorized representative, the person who administered the informed consent, and any other signatories according to local requirements. A copy of the signed informed consent will be given to the participant and the original will be placed in the participant's medical record. An entry must also be made in the participant's dated source documents to confirm that informed consent was obtained prior to any study-related procedures and that the participant received a signed copy.

Information regarding benefits for participants and information regarding provisions for treating and/or compensating participants who are harmed because of participation in the study can be found in the informed consent form.

Samples for optional pharmacogenetic analyses or other exploratory analyses will only be collected if the participant has voluntarily signed and dated a separate written consent form for this testing that has been approved by an IRB/IEC, after the nature of the testing has been explained and the participant has had an opportunity to ask questions. The separate written consent may be part of the main consent form. If the participant does not consent to the testing, it will not impact the participant's participation in the study.

3.2 Medical History

A complete medical history including demographics, history of tobacco, alcohol, and drug use will be taken at screening.

3.3 Drug and Alcohol Screen

Participants should have no history of clinically significant (per investigator's judgment) drug or alcohol abuse within the last 6 months.

Urine specimens will be tested at the screening visit for the presence of drugs of abuse. The panel for drugs of abuse will minimally include the drugs listed below. Any positive result must be assessed for clinical significance. These analyses will be performed by the certified central laboratory chosen for the study.

- Opiates
- Barbiturates
- Amphetamines
- Cocaine
- Benzodiazepines
- Alcohol
- Phencyclidine
- Methadone

3.4 Adverse Event Assessment

Please refer to Section [4.1](#).

3.5 Patient-Reported Outcomes

Participants may be asked to complete the self-administered patient-reported outcome (PRO) instrument (when allowed per local regulatory guidelines). Participants should be instructed to follow the instructions provided with the instrument and to provide the best possible response to each item. Site personnel shall not provide interpretation or assistance to participants other than encouragement to complete the tasks. Site personnel will encourage completion of the instrument at all specified visits and will ensure that a response is entered for all items. PRO assessments will include:

- Allodynia symptom checklist (ASC-12)
 - Allodynia is characterized by pain provoked by stimulation of the skin that would ordinarily not produce pain. Allodynia is associated with frequency, severity, disability and associated symptoms of migraine and maps to migraine biology. The ASC-12 measures overall allodynia and subtypes. Cutaneous allodynia affects patients with migraine and is associated with frequency, severity, disability and associated symptoms of migraine. ASC-12 includes 12 questions about the frequency of various allodynic symptoms in association with headache attacks. Each item is scored as "0" (i.e., very rarely or does not apply to me), "1" (less than half the time), or "2" (half the time or more).

- Columbia-Suicide Severity Rating Scale (C-SSRS)
 - The C-SSRS is a questionnaire used to assess suicide risk based on responses to series of questions on suicidal ideation and behavior.
- Headache assessments
 - The daily headache diary will collect data on presence of headache, headache duration, headache severity, headache characteristics and symptoms, acute medication use, and non-headache migraine symptoms.
- Activity Impairment in Migraine-Diary (AIM-D)
 - The AIM-D is an 11-item daily diary measure that assesses the impact of migraine and is comprised of two domains that evaluate performance of daily activities (7 items) and physical impairment (4 items). Participants are asked to rate the level of difficulty experienced in the past 24 hours with performance of daily activities (ie, difficulty with household chores, errands, leisure activities at home, leisure or social activities outside the home, strenuous physical activities, concentrating, and thinking clearly) and physical impairment (i.e., difficulty walking, moving body, bending forward, moving head) using the 6-point rating scale: "Not difficult at all," "A little difficult," "Somewhat difficult," "Very difficult," "Extremely difficult," and "I could not do it at all." Three items include a response of "I did not...", for example, "I did not have errands planned." In addition to the 2 domain scores, a total score using all 11 items can also be calculated. Each raw daily domain score, as well as the raw daily total score, are transformed to a 0-100 scale, with higher scores indicating greater impact of migraine (i.e., higher disease burden).
- MSQ v2.1 (Migraine-Specific Quality-of-Life Questionnaire [QOL])
 - The MSQ v2.1 is a 14-item questionnaire designed to measure health-related quality of life impairments attributed to migraine over the past 4 weeks. It is divided into 3 domains: Role Function Restrictive (RFR) assesses how migraines limit one's daily social and work-related activities; Role Function Preventive (RFP) assesses how migraines prevent these activities; and the Emotional Function (EF) domain assesses the emotions associated with migraines. Participants respond to items using a 6-point scale ranging from "none of the time" to "all of the time." Raw dimension scores are computed as a sum of item responses and rescaled to a 0 to 100 scale, where higher scores indicate better quality of life.
- PHQ-9 (Patient Health Questionnaire-9)
 - The PHQ-9 is a concise, self-administered, validated, screening and diagnostic tool for mental health disorder, which has been field-tested in office practice. The PHQ-9 consists of the 9 diagnostic criteria for depressive disorders in the past 2 weeks from the DSM-IV. Participants are asked to indicate the frequency with which they have been bothered by 9 symptoms of depressive disorders over the previous 2 weeks, on a 4-point scale: 0 (not at all), 1 (several days), 2 (more than half the days), and 3 (nearly every day). The total score ranges from 0 to 27 (from best to worst). A score of 15 to 19 is considered as moderately severe depression and 20 to 27 as severe depression.

- Work Productivity and Activity Impairment:Migraine (WPAI:MIGRAINE)
 - The WPAI:MIGRAINE will be used to assess work productivity specific to migraine. The measure uses a 1-week recall and contains 6 questions related to work productivity. The WPAI measures both presenteeism and absenteeism. The measure yields 4 scores, expressed as percentage of impairment, each ranging from 0% to 100%: percent work time missed, percent impairment while working, percent overall work impairment, and percent activity impairment due to migraine.
- Patient Satisfaction with Study Medication (PSSM)
 - The PSSM is a survey that assesses participants satisfaction with their study medication, using a single item and a 7-point rating scale ranging from extremely satisfied (0) to extremely dissatisfied (6). For this study, it will be worded to assess participant satisfaction with atogepant as addition to BOTOX.
- Patient Global Impression of Change (PGIC)
 - The PGIC is a single-item measure used to measure the participant's impression of overall change in migraine since the first dose of study intervention (atogepant). The measure uses a 7-point rating scale with responses ranging from "very much better" to "very much worse."
- Generalized Anxiety Disorder-7 (GAD-7)
 - GAD-7 is a self-reported 7-item questionnaire for screening and severity measuring of generalized anxiety disorder (GAD) in the past 2 weeks. GAD-7 measures severity of various signs of GAD according to reported response categories with assigned points. The GAD-7 items are: 1) nervousness, 2) inability to stop worrying, 3) excessive worry, 4) restlessness, 5) difficulty in relaxing, 6) easy irritation, and 7) fear of something awful happening. The GAD-7 is scored on a 4-point (0 - 3) scale where 'Not at all'=0, 'Several days'= 1, 'More than half the days'= 2, and 'Nearly every day'= 3. The total GAD-7 score range is 0 - 21 (from 'best to worst'), and a score of 10 or greater indicates a reasonable cut point for identifying cases of GAD. Cut points of 5, 10, and 15 might be interpreted as representing mild, moderate, and severe levels of anxiety on the GAD-7.
- Patient-Reported Outcomes Measurement Information System (PROMIS) v2.0 Cognitive Function Abilities Short-Form 6a
 - The PROMIS Cognitive Function and Cognitive Function Abilities Subset item banks assess patient-perceived cognitive deficits. Facets include mental acuity, concentration, verbal and nonverbal memory, verbal fluency, and perceived changes in these cognitive functions. Extent to which cognitive impairments interfere with daily functioning, whether other people observe cognitive impairments, and the impact of cognitive dysfunction on quality of life are also assessed.

On Day 1, the PRO instrument should be completed prior to drug administration and prior to any discussion of adverse event (AE) or any review of laboratory findings.

The participant should complete the questionnaire before site personnel perform any clinical assessments and before any interaction with site personnel has occurred to avoid biasing the participant's response.

3.6 Pharmacokinetic Sampling

Not applicable.

3.7 Biomarker Research Sampling

Biospecimens (whole blood and saliva) will be collected to support the biomarker research objectives of the study. Please refer to the Study Activities Schedule in Appendix D for the schedule of biomarker research sample collections. Assessments may include, but are not limited to, biomarkers related to the pathway(s) targeted by the study drug, or those believed to be related to the disease(s) being studied. The information learned from analyzing these samples may be used to investigate factors influencing response to treatment, scientific questions related to chronic migraine, and/or in the development of new therapies and diagnostic tests.

DNA/RNA isolated from whole blood may be analyzed to determine specific genetic mutations in patients with migraine and related conditions as well as determine if any of these mutations are associated with response to treatment with BOTOX and/or atogepant (or drugs of this class). In addition, plasma and saliva may be analyzed to determine concentrations of calcitonin gene-related peptide (CGRP) or related neuropeptides to determine if changes in these peptides are related to migraine or associated with response to treatment with BOTOX and/or atogepant (or drugs of this class).

All biomarker samples should be labeled and shipped as outlined in the study-specific laboratory manual. AbbVie (or people or companies working with AbbVie) will store the samples and data in a secure storage space with measures to protect confidentiality. The samples may be retained while research on atogepant and/or onabotulinumtoxinA (BOTOX) (or drugs of this class) or migraine and related conditions continues, but for no longer than 20 years after study completion, or per local requirement.

3.8 12-Lead Electrocardiogram

12 Lead Electrocardiogram (Single Only)

Resting 12-lead electrocardiogram (ECG) will be obtained singly as specified in Appendix D of the study protocol.

The ECG acquired prior to atogepant dosing will serve as the baseline measurements for clinical assessment.

When an ECG is scheduled at the same time as a blood collection, the ECG will be obtained prior to the blood collection. ECGs occurring near meals will take place prior to meals.

ECGs will be acquired after the participant has been in the supine position for at least 5 minutes. Participants will be instructed to remain completely stationary (no talking, laughing, deep breathing,

sleeping, or swallowing) for approximately 10 seconds during the ECG recording. While ECGs are being acquired, participants and staff are prohibited from having devices (e.g., cellular telephones, fans, heaters, etc.) that emit electrical interference in the room.

ECG Safety Review

Each ECG will be evaluated by an appropriately trained investigator at the study site (the "local reader"). The local reading of the ECG will be used by the investigator to determine participant eligibility and safety assessments, including AE determination and management, and decision on whether a participant will be discontinued from the study.

The local reader will sign and date all the ECGs collected in this study and provide a global interpretation for each ECG using the following categories:

- Normal ECG
- Abnormal ECG Not clinically significant (NCS)
- Abnormal ECG Clinically significant (CS)
- Unable to evaluate

All local reader evaluations of ECGs will be entered into the source documents. If the global interpretation (i.e., central reader interpretation) is abnormal (NCS or CS), the local reader will provide further information (e.g., sinus bradycardia, arrhythmia). The QT interval corrected for heart rate (QTc) using Fridericia's formula (QTcF) will be calculated and documented for all ECGs.

All ECGs will be transmitted to the central ECG reading center regardless of readability. All ECG source documentation will be retained at the study site. The automatic cardiograph reading (i.e., cardiograph-generated measurements and interpretations) will not be collected for analysis.

3.9 Height and Weight

Height will be measured at Screening only. Body weight will be measured at scheduled visits as specified in Section 2.1. The participant will wear lightweight clothing and no shoes during weighing.

3.10 Vital Signs

Vital sign determinations of systolic and diastolic blood pressure, pulse rate, respiratory rate, and body temperature will be obtained at visits as specified in Section 2.1. Blood pressure and pulse rate should be measured after the participant has been sitting for at least 3 minutes.

Measurements should be assessed consistently throughout the study. Vital sign measurements determined prior to dosing on Day 1 or specify timing will serve as baseline.

3.11 Physical Examination

A complete physical examination, including height (at Screening only) and weight, will be performed at the designated study visits as specified in Section 2.1. The physical examination performed at Screening will serve as the baseline physical examination for the entire study. Physical examination abnormalities noted at screening, prior to the first dose of study drug, should be recorded in the participant's medical history. Any significant physical examination findings after the first dose will be recorded as AEs. All findings, whether related to an AE or part of each participant's medical history, will be captured on the appropriate electronic case report form (eCRF) page.

At any time, a symptom-directed physical examination can be performed as deemed necessary by the investigator.

3.12 Dispense Study Drug

Study drug (atogepant) will be dispensed to participants beginning at Baseline (Day 1) and as specified in Section 2.1. The first dose of atogepant study drug will be administered after all other baseline (Day 1) procedures are completed. At the visits specified in Section 2.1, the site personnel will review and retain a copy of the dosing diary, review returned study drug kits, and empty study drug packaging to verify compliance.

Each site will be responsible for maintaining drug accountability records including product description, manufacturer, and lot numbers for all non-investigational products dispensed by the site.

Study drug (i.e., atogepant tablets) can be taken with or without food.

3.13 Clinical Laboratory Tests

The blood samples for serum chemistry tests will be collected prior to study drug intake (except for the Screening Visit). An 8-hour fast is preferred but not required prior to blood sample collection. The baseline laboratory test results for clinical assessment for a particular test will be defined as the last measurement prior to the initial dose of study drug.

A certified laboratory will be utilized to process and provide results for the clinical laboratory tests. Laboratory reference ranges will be obtained prior to the initiation of the study.

Instructions regarding the collection, processing, and shipping of these samples will be provided by the central laboratory.

If a laboratory test value is outside the reference range and the investigator considers the laboratory result to be clinically significant, the investigator will:

- repeat the test to verify the out-of-range value;
- follow the out-of-range value to a satisfactory clinical resolution; or

- discontinue the participant from the study or require the participant to receive treatment; in this case, the laboratory result will be recorded as an AE.

Clinical Laboratory Tests		
Hematology	Clinical Chemistry ^a	Urinalysis
Hematocrit Hemoglobin Red blood cell (RBC) count Red blood cell indices (mean corpuscular volume, mean corpuscular hemoglobin, mean corpuscular hemoglobin concentration) White blood cell (WBC) count Neutrophils Bands Lymphocytes Monocytes Basophils Eosinophils Platelet count (estimate not acceptable)	Blood urea nitrogen (BUN) Creatinine Creatine kinase Total bilirubin Direct and indirect bilirubin Gamma-glutamyl transferase (GGT) Lactate dehydrogenase (LDH) Alanine aminotransferase (SGPT/ALT) Aspartate aminotransferase (SGOT/AST) Alkaline phosphatase Sodium Potassium Calcium Inorganic phosphorus Total protein Glucose Albumin Chloride Bicarbonate/CO ₂ Uric acid Cholesterol Triglycerides Estimated glomerular filtration rate (GFR) Calculation	Specific gravity Ketones pH Protein Blood Microscopic examination including red blood cells/high-power field, white blood cells/high-power field, and casts/low-power field ^b Glucose
		Other Tests
		Urine human chorionic gonadotropin ^c Follicle-stimulating hormone ^d Marker of Inflammation: TNF α – Serum ^e Marker of Inflammation: C- Reactive Protein (CRP) ^e Adipokine Hormones: Adiponectin - serum or plasma ^e Adipokine Hormones: leptin - serum or plasma ^e Hormones: GLP-1 ^e Glucose metabolism: HbA1c - separate collection ^e Lipid profile: LDL ^e Lipid profile: HDL ^e Lipid profile: VLDL ^e Lipid profile: NEFAs (FFAs) ^e Urine drug screen: alcohol, opiates, barbiturates, amphetamines, cocaine, benzodiazepines, alcohol, phencyclidine, methadone
Coagulation		
Prothrombin time (PT)/INR		
Serology^b		
Hepatitis B surface antigen ^b Anti-hepatitis C antibody ^b		

FFA = free fatty acids; GLP-1 = glucagon-like peptide 1; HbA1c = hemoglobin A1c; HDL = high-density lipoprotein; INR = international normalized ratio; LDL = low-density lipoprotein; NEFA = non-esterified fatty acids; TNF α = TNF alpha; VLDL = very low-density lipoprotein

- All chemistries should be performed at all visits.
- Performed only at screening.
- Pregnancy testing is not required for females of nonchildbearing potential. Test materials are provided by central lab, but testing is performed locally.
- Performed only at screening for females aged ≤ 55 years with no menses for 12 months without an alternative medical cause for menopause.
- Performed only at Visit 2 and Visit 8.

Clinical Laboratory Kits for Incidences of Elevated ALT or AST		
ALT/AST Confirmation	ALT/AST Investigation	ALT/AST Follow-up
Chemistry Blood urea nitrogen (BUN) Creatinine Creatine kinase Total bilirubin Direct and indirect bilirubin Gamma-glutamyl transferase (GGT) Lactate dehydrogenase (LDH) Alanine aminotransferase (SGPT/ALT) Aspartate aminotransferase (SGOT/AST) Alkaline phosphatase Sodium Potassium Calcium Inorganic phosphorus Total protein Glucose Albumin Chloride Bicarbonate/CO ₂ Uric acid Cholesterol Triglycerides Estimated glomerular filtration rate (GFR) Calculation Hematology Hematocrit Hemoglobin Red blood cell (RBC) count Red blood cell indices (mean corpuscular volume, mean corpuscular hemoglobin, mean corpuscular hemoglobin concentration) White blood cell (WBC) count Neutrophils Bands Lymphocytes Monocytes Basophils Eosinophils Platelet count (estimate not acceptable)	Chemistry^a Blood urea nitrogen (BUN) ^a Creatinine ^a Creatine kinase ^a Total bilirubin ^a Direct and indirect bilirubin ^a Gamma-glutamyl transferase (GGT) ^a Lactate dehydrogenase (LDH) ^a Alanine aminotransferase (SGPT/ALT) ^a Aspartate aminotransferase (SGOT/AST) ^a Alkaline phosphatase ^a Sodium ^a Potassium ^a Calcium ^a Inorganic phosphorus ^a Total protein ^a Glucose ^a Albumin ^a Chloride Bicarbonate/CO ₂ ^a Uric acid ^a Cholesterol ^a Triglycerides ^a Estimated glomerular filtration rate (GFR) Calculation ^a Serology^a Hepatitis B surface antigen ^a Other Tests Anti-hepatitis A IgM ^a Anti-hepatitis B Core IgM ^a Hepatitis C antibody ^a Hepatitis C quantitative RNA by PCR ^a Anti-hepatitis E IgM ^a Cytomegalovirus, IgM antibody ^a Epstein-Barr Virus, IgM antibody ^a Ceruloplasmin ^b Serum Iron ^b Alpha-Fetoprotein ^b Serum Electrophoresis ^b Antinuclear antibody (ANA) ^b Anti-liver – Kidney microsomal antibody ^b Anti-Soluble liver antigen ^b Anti-Mitochondrial antibody ^b Mitochondrial antibodies ^b Serum alpha-I anti trypsin ^b IgG-1 ^b	Chemistry Blood urea nitrogen (BUN) Creatinine Creatine kinase Total bilirubin Direct and indirect bilirubin Gamma-glutamyl transferase (GGT) Lactate dehydrogenase (LDH) Alanine aminotransferase (SGPT/ALT) Aspartate aminotransferase (SGOT/AST) Alkaline phosphatase Sodium Potassium Calcium Inorganic phosphorus Total protein Glucose Albumin Chloride Bicarbonate/CO ₂ Uric acid Cholesterol Triglycerides Estimated glomerular filtration rate (GFR) Calculation

Clinical Laboratory Kits for Incidences of Elevated ALT or AST		
ALT/AST Confirmation	ALT/AST Investigation	ALT/AST Follow-up
Coagulation Prothrombin time (PT)/INR Other Tests Serum Ethanol Serum Acetaminophen Urine Drugs of Abuse (not including tramadol) Oxycodone Screen Banked Serum Future Testing	Anti-smooth muscle antibody ^b Anti- LC1 ^b	

- a. Mandatory test.
b. Optional test.

Pregnancy Tests (Urine)

Pregnancy testing should not be performed for postmenopausal women.

A urine pregnancy test will be performed at each visit for all female participants of childbearing potential.

More frequent pregnancy tests can be performed throughout the study at the investigator's discretion or if required per local/country requirements.

- If the urine pregnancy test at Screening is negative, then dosing with study drug may begin.
- If the Day 1 or post-baseline urine pregnancy test is positive, dosing with study drug must be withheld.
- For remote visits such as Visit 9 (Follow-up or End of Study) and for women of childbearing potential only, a urine pregnancy test must be performed within 48 hours prior to the remote visits. Investigators/site staff will provide participants with FDA-approved urine pregnancy tests and corresponding written instructions to be used at home by participants for the remote study visits. Sites are required to verbally review testing instructions with all participants.

Clinical Chemistry

A minimum 8-hour fast prior to study drug intake is preferred but not required for blood samples to be drawn for chemistry. If a participant does not fast, the nonfasting status will be recorded in study source documentation.

Urinalysis

Dipstick urinalysis will be completed by the central laboratory at all required visits. Specified abnormal macroscopic urinalyses defined as leukocytes, nitrite, protein, ketones, or blood greater than negative, or glucose greater than normal will be followed up with a microscopic analysis at the central laboratory.

[figure not shown]

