3.4 Biomarker Research Endpoints

Optional fluid biomarker collection for genomics (single serum/plasma sample for DNA and RNA at Visit 2), and CGRP level (saliva and plasma sample at Visits 2, 5, and 8). An assessment of allodynia (via an allodynia symptom checklist, such as ASC-12)⁵ will be completed at Baseline. Additionally, certain laboratory assessments at Visits 2 and 8 (Section 3.13 of [Appendix F](#), footnote d) will be performed to provide information on the weight loss observed in previous trials with atogepant (see QULIPTA™ Package Insert).

Further details regarding the biomarker research rationale and collection time points are located in the Operations Manual, Section 3.7.

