10.3 Analysis of Laboratory Data

Data collected from central laboratories, including additional laboratory testing due to an SAE, will be used in all analyses, except for Baseline where SAE-related laboratory assessments on or before the first dose of study drug will be excluded. The clinical laboratory tests defined in the protocol operations manual (e.g., hematology, clinical chemistry, and urinalysis) will be summarized.

Each laboratory variable will be summarized for all time points (starting with Baseline) with the number of non-missing observations, mean and standard deviation, median, Q1, Q3, minimum and maximum. Mean change from baseline to each applicable post-baseline visit will be summarized, with the number of observations, baseline mean, and visit mean. The change from baseline mean will be presented for the mean change from baseline. In addition, descriptive statistics for values and changes from the baseline values in conventional units at each assessment time point will be presented for selected clinical laboratory parameters listed in [Appendix E](#). A description of reporting the lab values in conventional units in patient narratives (along with the standard reporting in SI units) is presented at the end of [Appendix E](#).

Changes in laboratory parameters will be tabulated using shift tables categorized as low, normal, or high based on the normal ranges of the laboratory used for each sample. A shift table will be provided to summarize shifts from baseline to the final post-baseline value.

Laboratory abnormalities will be evaluated based on Potentially Clinically Significant (PCS) criteria (Appendix Table D-1). For each laboratory PCS criterion, the number and percentage of participants who have a laboratory value meeting the criteria will be summarized. Listings will be provided to summarize participant-level laboratory data for participants meeting PCS criteria.

In addition, ALT, AST, alkaline phosphatase, and total bilirubin will be categorized in Table D-2. The number and percentage of participants meeting each of the criteria for postbaseline hepatic laboratory abnormalities listed in Table D-2 will be summarized. The percentages will be calculated relative to the number of participants with at least 1 available postbaseline assessment. The numerator will be the total number of participants having at least 1 postbaseline value that meets the specific category during the study. A supportive listing will also be provided.

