Appendix D. Potentially Clinically Significant Criteria for Safety Endpoints

The potentially clinically significant (PCS) criteria for clinical laboratory parameters are described in Table D-1, the criteria for hepatic laboratory abnormalities are described in Table D-2, the PCS criteria for vital sign findings are described in Table D-3, the PCS criteria for ECG parameters are described in Table D-4, and the Clinical Interest Criteria for ECG parameters are described in Table D-5.

Table D-1. Potentially Clinically Significant Criteria for Clinical Laboratory Parameters

Category	Parameter	SI Unit	PCS Criteria	
			PCS Low	PCS High
Chemistry	Albumin	g/L	$< 0.8 \times \text{LLN}$	$> 1.2 \times \text{ULN}$
	Alanine aminotransferase	U/L	—	$\geq 3.0 \times \text{ULN}$
	Alkaline phosphatase	U/L	—	$\geq 3.0 \times \text{ULN}$
	Aspartate aminotransferase	U/L	—	$\geq 3.0 \times \text{ULN}$
	Bicarbonate	mmol/L	$< 0.9 \times \text{LLN}$	$> 1.1 \times \text{ULN}$
	Bilirubin, total	$\mu\text{mol/L}$	—	$\geq 1.5 \times \text{ULN}$
	Blood urea nitrogen	mmol/L	—	$> 1.5 \times \text{ULN}$
	Calcium	mmol/L	$< 0.9 \times \text{LLN}$	$> 1.1 \times \text{ULN}$
	Chloride	mmol/L	$< 0.9 \times \text{LLN}$	$> 1.1 \times \text{ULN}$
	Cholesterol, total	mmol/L	—	$> 1.6 \times \text{ULN}$
	Creatinine	$\mu\text{mol/L}$	—	$> 1.5 \times \text{ULN}$
	Creatine kinase	U/L	—	$> 2.0 \times \text{ULN}$
	Estimated glomerular filtration rate	mL/sec/1.73m^2	< 1	—
	Glucose, nonfasting	mmol/L	$< 0.8 \times \text{LLN}$	$> 2.0 \times \text{ULN}$
	Lactate dehydrogenase (LDH)	U/L	—	$> 3.0 \times \text{ULN}$
	Phosphorus	mmol/L	$< 0.9 \times \text{LLN}$	$> 1.1 \times \text{ULN}$
	Potassium	mmol/L	$< 0.9 \times \text{LLN}$	$> 1.1 \times \text{ULN}$
	Protein, total	g/L	$< 0.9 \times \text{LLN}$	$> 1.1 \times \text{ULN}$
	Sodium	mmol/L	$< 0.9 \times \text{LLN}$	$> 1.1 \times \text{ULN}$
	Triglycerides	mmol/L	—	$> 2.0 \times \text{ULN}$
	Uric acid	$\mu\text{mol/L}$	—	$> 1.2 \times \text{ULN}$

Category	Parameter	SI Unit	PCS Criteria	
			PCS Low	PCS High
Hematology	Basophils, absolute cell count	$10^9/L$	—	$> 2.0 \times ULN$
	Eosinophils, absolute cell count	$10^9/L$	—	$> 2.0 \times ULN$
	Hematocrit	Ratio	$< 0.9 \times LLN$	$> 1.1 \times ULN$
	Hemoglobin	g/L	$< 0.9 \times LLN$	$> 1.1 \times ULN$
	Lymphocytes, absolute cell count	$10^9/L$	$< 0.7 \times LLN$	$> 1.3 \times ULN$
	Monocytes, absolute cell count	$10^9/L$	$< 0.5 \times LLN$	$> 2.0 \times ULN$

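### The planned change-from-baseline summary of the Visit 2 and Visit 8 weight-loss markers that respond to meals (NEFA, VLDL, GLP-1) makes no use of fasting status

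*Protocol*

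**What the plan says.** Protocol 3.4 (Biomarker Research Endpoints) states that certain laboratory tests at Visits 2 and 8 "will be performed to provide information on the weight loss observed in previous trials with atogepant". It gives no other purpose for them. In the table in Operations Manual 3.13 (Protocol Appendix F) these are the tests noted "Performed only at Visit 2 and Visit 8": TNF-alpha, CRP, adiponectin, leptin, GLP-1, HbA1c, LDL, HDL, VLDL and NEFA. (Protocol 3.4 points to footnote d for them. In the table they carry footnote e, and d is the FSH note.)

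On fasting, Operations Manual 3.13 says "An 8-hour fast is preferred but not required prior to blood sample collection" and repeats the preference under Clinical Chemistry, with no exception for this panel. It continues: "If a participant does not fast, the nonfasting status will be recorded in study source documentation".

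Triglycerides and glucose are in the routine chemistry column, where the note is "All chemistries should be performed at all visits".

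SAP 10.3 covers the laboratory tests defined in the Operations Manual with one general rule: "Mean change from baseline to each applicable post-baseline visit will be summarized, with the number of observations, baseline mean, and visit mean". It has no stratum, covariate or sensitivity analysis for fasting. The SAP's only mention of fasting state is the potentially clinically significant (PCS) criterion labelled "Glucose, nonfasting" in Table D-1.

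**The concern.** NEFA, VLDL and GLP-1 are each measured once before and once during treatment, in a single-arm study. A participant who is fasted at one visit and fed at the other shows a change that has nothing to do with atogepant. If the share of fasted participants drifts between the two visits, the mean change moves with it, and no control arm shows that drift.

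The plan comes close to dealing with this. It treats fasting as relevant enough to prefer it and to have exceptions noted, but the note is not routed to where the analysis could use it. Two details make it harder to use:

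- Only non-fasting is to be written down, so a missing note may mean either fasted or not asked.
- The recording sentence stands under Clinical Chemistry, while NEFA, VLDL and GLP-1 are listed under Other Tests. It is therefore not certain that the rule covers the panel.

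At stake is the interpretation of three exploratory analytes for the one purpose Protocol 3.4 gives them.

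**Working it through.** **Inputs from the documents.** The fast is optional, status goes to source, the panel is taken at two visits, and the summary is an unconditional mean change (sections cited above). The expected number of completers is 60: 75 enrolled with 20% early termination gives 75 x 0.80 = 60 (Protocol 7.7). The documents give no figure for fasting shares or meal effects, so there is no plan figure to reproduce.

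**Assumptions.** That these three analytes respond to meals is general knowledge and is not stated in the documents. The fasting shares and meal effects below are illustrative.

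**Step 1: bias in the mean.** Let s be the fasted share at a visit and f the factor by which a meal multiplies the analyte. Relative to the all-fasted mean, the visit mean is s + (1 - s) x f. With no drug effect, the apparent change is the ratio of the two visit means minus 1. For f = 0.5:

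- 70% fasted: 0.70 + 0.30 x 0.5 = 0.85
- 50% fasted: 0.50 + 0.50 x 0.5 = 0.75
- 40% fasted: 0.40 + 0.60 x 0.5 = 0.70

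Going from 70% to 50% gives 0.75/0.85 - 1 = -11.8%. Going from 70% to 40% gives 0.70/0.85 - 1 = -17.6%. The corresponding means are 1.075, 1.125 and 1.15 for f = 1.25, and 1.30, 1.50 and 1.60 for f = 2.

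| Fasted share, Visit 2 to Visit 8 | f = 0.5 | f = 1.25 | f = 2 |
|---|---|---|---|
| 70% to 70% | 0% | 0% | 0% |
| 70% to 50% | -11.8% | +4.7% | +15.4% |
| 70% to 40% | -17.6% | +7.0% | +23.1% |
| 50% to 70% | +13.3% | -4.4% | -13.3% |
| 40% to 70% | +21.4% | -6.5% | -18.8% |

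The bias depends on the difference in shares. It is zero when they are equal and changes sign when the share rises.

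**Step 2: variance.** Let the paired change have SD 1 when meal state is constant, let a meal shift the value by m of those SDs, and let p2 and p8 be the non-fasting shares, independent between visits. Then bias = m x (p8 - p2) and SD = sqrt(1 + m^2 x [p2(1 - p2) + p8(1 - p8)]). With equal shares of 30% to 50% the bias is zero and the SD rises as follows:

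- m = 0.5: by 5% to 6%
- m = 1: by 19% (sqrt(1.42) = 1.192) to 22% (sqrt(1.50) = 1.225)
- m = 2: by 64% to 73%

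If individual participants are consistent in their habits, the increase is smaller.

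**Step 3: does using the status remove the bias?** With n = 60 and no meal effect, the 95% half-width of the mean change is 0.26 SD. With 30% then 50% non-fasting, the bias is 0.20 SD for m = 1 and 0.40 SD for m = 2. In 5,000 simulated trials with no true change, the unadjusted 95% interval excluded zero in 24% (m = 1) and 44% (m = 2). After adjustment for the change in fasting status, the mean was about 0.00 in both cases and the interval excluded zero in 4.8% and 4.9%. Restricting to participants with the same status at both visits also gave a mean of about 0.00.

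**The case against.** Much of the case on the other side stands.

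- A reader might infer that the confounding cannot be corrected. The documents do not support that. Non-fasting status is to be recorded in source, so it can be abstracted and used, and step 3 shows that using it works.
- Nor do the documents show that status is confined to source. Collection instructions come from the central laboratory (Operations Manual 3.13), and a study-specific laboratory manual is mentioned (3.7). Those documents, the eCRF and the requisition are not available here, and a requisition may already capture fasting. The claim can only be that the protocol and SAP name no such field.
- A reader might infer that the mean change must be biased. Both visits carry the same instruction, and nothing in the documents says that fasting will fall or rise between them. Zero belongs in the range.
- A reader might put triglycerides and glucose in the same position. They follow the same optional-fast rule, but they are chemistry tests taken at all visits, so the one-pair argument does not apply. The SAP already labels the glucose PCS criterion as nonfasting, and Table D-1 has no PCS criterion for NEFA, VLDL or GLP-1.
- A reader might infer that the whole panel fails its purpose, or that matched fasting would isolate a drug effect. Neither follows. The point concerns three of the ten tests, and body weight is summarised directly (SAP 10.4, with a 7% change criterion in Table D-3). In a single-arm study even a matched change is not causal.

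What remains is that the documents, followed as written, leave a measurable and avoidable source of change in these three analytes without any planned use of the information that would address it.

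**Conclusion.** The point holds as a minor one. For NEFA, VLDL and GLP-1 the current plan does not separate meal state from change on treatment, although status noted in source can still be used.

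The bias in the mean change is zero if the fasted share is the same at Visits 2 and 8. On assumed shares of 70% then 40% to 50%, it is about -12% to -18% if a meal halves the analyte and +15% to +23% if a meal doubles it, with opposite signs if the share rises. Equal shares leave only extra variance. These sizes rest on assumed shares and meal factors, and on the general expectation that the three analytes respond to meals.

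The panel is exploratory and SAP 10.3 plans only descriptive summaries. The primary safety conclusions, the efficacy endpoints and the sample-size statement are not affected.

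**What to change.** Bring fasting status at Visits 2 and 8 into the database: yes/no, and hours since last meal where available. Where the eCRF or laboratory data do not already hold it, abstract it from source before lock, and keep a missing note distinct from a confirmed fast.

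Add to SAP 10.3 a summary of the change in NEFA, VLDL and GLP-1, and of the Visit 2 to Visit 8 change in triglycerides and glucose, among participants with the same fasting status at both visits, or adjusted for status. Show it alongside the unrestricted summary, and report the fasted share at each visit so that a reader can see whether it moved.

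The cost is one data field, some source abstraction and one SAP sentence. The downside is a smaller n in the matched summary. If status is independent between visits, 70% fasted at both gives 0.7 x 0.7 + 0.3 x 0.3 = 0.58, or about 35 of 60 completers; 70% then 50% gives 0.7 x 0.5 + 0.3 x 0.5 = 0.50, or 30 of 60. Consistent habits would leave more. The adjusted version keeps every participant with known status at both visits.
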